Aim 1, Hypothesis 1: Dyads initially randomized to the TIP-C+SMSH will report lower depression, anxiety, and summed severity of other symptoms at weeks 1-12, 13, and 17, and lower unscheduled health services use, higher self-efficacy and social support, and lower caregiver burden at weeks 13 and 17 as compared to those initially randomized to the SMSH alone. This hypothesis will be tested using statistical model #1 that relates repeated measures of the survivor or caregiver outcome y (one at a time) to the group assignment variable xx_1 , outcome at baseline xx_2 , time entered as a class variable to model potentially non-linear patterns, and other covariates. For normally distributed outcomes, this model will be fit as a linear mixed effects model (LME). Generalized linear mixed effects (GLME) modeling will be used if outcome is not normally distributed and cannot be normalized using transformations. For health service use, statistical model #1 will be implemented as a GLME model with Poisson distributed errors, or as a zero-inflated Poisson or negative Binomial model based on the distribution of the counts of different health services uses. Each type of health services use (e.g., hospitalizations, ED visits) will be analyzed separately. The explanatory variables including study group will be evaluated as predictors of zero inflation (whether or not the count is zero), and also as predictors of the magnitude of the count when it is not zero. The main effects of the group variable xx_1 will be tested.

Aim 2, Hypothesis 2: Dyads where survivors do not respond to the SMSH alone during weeks 1-4 and have TIP-C added during weeks 5-12, will report lower depression, anxiety, and summed severity of other symptoms at weeks 5-12, 13, and 17, and lower unscheduled health services use, higher self-efficacy and social support, and lower caregiver burden at weeks 13 and 17 as compared to those who are re-randomized to continue with the SMSH alone. The strategy described under the analyses for Aim 1 will be implemented for the repeated outcome measures during weeks 5-12 and weeks 13 and 17 that will be related to group assignment from the second randomization, symptom severity during week 4, time, and covariates.

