Mediation analyses for Aims 1 and 2. To test for mediation, the study group will be treated as the independent variable, and each of the potential mediators (one at a time) will be tested for their effect on the symptom outcome variable at weeks 13 and 17, with the baseline measure of that respective symptom outcome variable treated as a covariate. Caregiver burden will be tested only at the individual level, but social support and self-efficacy will be tested at the individual and dyadic levels. We will use a bias corrected bootstrapping analytic strategy^{267,268} based on 5000 bootstrap samples to estimate confidence intervals around the indirect effect of study group on the outcome variable, through the mediator. To establish mediation, the 95% confidence interval around the indirect effect must not include 0.

Aim 3 examines the dyadic interdependence in outcomes between survivors and caregivers. This interdependence will be modeled and tested with the actor-partner interdependence mediation model (APIMem)²⁶⁹ in structural equation modeling. The APIMem estimates three classes of effects: actor effects (e.g., person A independent variable (IV) \rightarrow person A dependent variable (DV)), caregiver (partner) effects (e.g., person A IV \rightarrow person B DV), and mediation effects (e.g., person A IV \rightarrow person B Mediator \rightarrow person A DV) in an omnibus model. These models will specify correlations between the survivors' and caregivers' IVs as well as covariances between the error terms of the mediators and outcome variables, recognizing that these residuals will covary between dyad members due to unmeasured common causes. We will fit both a saturated version of the model in which all actor, partner, and mediation effects are free to vary and compare that with a

constrained model in which the effects for one dyad member are constrained equal to the corresponding effects of the other dyad member. The χ^2 difference test will determine whether the more parsimonious constrained model or the unconstrained model will be interpreted. This test will also indicate whether the effect for survivors is significantly different from that of caregivers. These models will test whether baseline to week 17 changes in survivors' outcomes of depression, anxiety and summed severity of other symptoms are mediated by the intervening (week 13) state or caregivers' outcomes or potential covariates.

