6.0 MEASURES/DATA COLLECTION INSTRUMENTS

Describe all forms, questionnaires, instruments or other specific methods used to collect data. Include complete copies of all forms, interview guides, survey questionnaires, in Appendix I.

Measures

Patient Reported Outcomes Measurement Information System (PROMIS)²⁴⁹ measures are suitable for both survivors and caregivers, have been developed using sophisticated measurement techniques, tested with over 21,000 individuals, calibrated to produce T-scores based on the general population, and are available in either English or Spanish. The available short forms have evidence of good reliability and validity.²⁴⁹ Our other measures also have good reliability ($\alpha > .80$)^{41,84,178,205} and validity, have been translated²⁴⁰ and tested with Spanish speaking participants in our pilot studies.³¹

Primary outcomes.

Caregivers' and survivors' symptoms will be measured using the adapted General Symptom Distress Scale (GSDS),^{124,250} a brief instrument that allows for a quick assessment of symptoms, which is especially important during weekly calls. It evaluates 15 symptoms: shortness of breath, nausea, vomiting, pain, sleep difficulties, bowel problems, numbness or tingling, skin rashes or sores, swelling in hands and feet, difficulty concentrating, poor appetite, cough, depression, anxiety, fatigue. Respondents indicate presence of each symptom (yes/no) and rate their severity on the scale from 1 to 10. The ability to manage symptoms is also assessed on a scale from 1=cannot manage to 10=can manage extremely well. The GSDS has good test-retest and internal consistency reliability and predictive and construct validity in both English and Spanish.²⁵⁰ The 0-10 ratings of depression and anxiety and the summed severity of other 13 symptoms will be derived at each weekly contact, baseline, 13, and 17 week interviews.

Survivors' symptom response on depression and/or anxiety during weeks 1-4 as a criterion for rerandomization.

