Response will be assessed using the depression and anxiety items of the GSDS administered during weekly calls to survivors. Based on the inclusion criteria and established and validated symptom cut points,²²⁴ survivors will enter with moderate or severe depression and/or anxiety (one symptom or both). The cut-points are anchored in how much symptoms are distressing the participant by interfering with enjoyment of life, social relationships, and general daily activities. Participants indicate the severity/distress from 1 to 10. For depression, the mild category corresponds to a severity score of 1, the moderate category corresponds to scores 2-3, and scores of 4-10 fall into the severe category. For anxiety, the mild category is

severity of 1-3, the moderate category corresponds to scores 4-5, and the severe category is 6-10. Survivors who start at severe or moderate on depression and/or anxiety symptoms at intake and end at a lower category by the week 4 observation will be called **responders to the intervention**.²²⁸ If a symptom was mild at intake, symptom response would not be applicable. Because responders demonstrate substantial improvement anchored to symptom distress after 4 weeks, responders will continue with the SMSH only intervention for another 8 weeks. **Non-responders to the intervention** are survivors who do not respond on either or both symptoms.^{224,251,252} Non-responding survivors and their caregivers will be re-randomized to either continue with the SMSH alone for 8 weeks to give it additional time or add TIP-C for 8 weeks to rigorously test the value added by the more intensive intervention in Aim 2. Total intervention time is 12 weeks.

Caregivers' and survivors' depression and anxiety. PROMIS-short forms 8: depression and anxiety²⁵³⁻²⁵⁶ will be administered at baseline, 13 and 17 week telephone interviews to provide greater detail and precision in the measurement of these outcomes, as compared to single GSDS items administered in weekly calls. We chose 8-item short forms to minimize respondent burden while maintaining measurement precision.

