Secondary outcomes. Secondary outcomes are caregivers' and survivors' hospitalizations, urgent care or ED visits during the study. In baseline, week 13 and 17 interviews over the telephone, each dyad member will be asked to recall ED visits and admissions to hospitals and, if they occurred, their reasons and duration. Recall period will be 3 months in baseline and week 13, and 1 month in week 17 interviews. Extensive previous research²⁻⁵ documents self-report is a reliable and valid method to collect health services use data especially when standardized methods are used and the recall period is short, as in this project. Self-report is the only reasonable and cost-effective way to assess healthcare use, as it would be impossible to access health (medical) records across the multiple systems and payers used by participants in this study.

Potential mediators.

Caregivers' and survivors' self-efficacy. PROMIS 4-item short forms (sf) will be administered in interviews.²⁵³⁻²⁵⁶ Self-efficacy specific to symptom management will be captured by the GSDS item described above.

Caregivers' and survivors' social support. PROMIS 4-item-sf for emotional support and PROMIS Informational Support 4a will be used in interviews.²⁵³⁻²⁵⁶

Caregiver Reaction Assessment Tool.²⁵⁷ This caregiver burden tool was developed and validated with caregivers of patients with chronic conditions. It has 5 subscales: impact on schedule, caregiver's esteem, family support, impact on health, and impact on finances, with Cronbach's alphas exceeding 0.70.

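### For Aim 2 the outcome model adjusts for week-4 severity but the mediation model only for week-0 severity, so the Aim 2 indirect effect may be biased, in a direction the documents do not fix

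*Combined protocol and SAP*

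**What the plan says.** The text below stands in section 5.0 (Analytic Methods) and is repeated in section 8.0 of the combined protocol and SAP.

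- **Aim 1 outcome model:** adjusts for the outcome at baseline.
- **Aim 2 outcome model:** names a different starting value. Outcomes are related to "group assignment from the second randomization, symptom severity during week 4, time, and covariates".
- **Mediation:** one paragraph, headed "Mediation analyses for Aims 1 and 2", covers both aims. Each mediator is tested for its effect on the week-13 and week-17 symptom, "with the baseline measure of that respective symptom outcome variable treated as a covariate". No week-4 term and no other covariates are named.
- **Decision rule:** a bias-corrected bootstrap interval "based on 5000 bootstrap samples". Mediation is established if "the 95% confidence interval around the indirect effect must not include 0".
- **Timing:** the schedule of events in section 9.0 places baseline at week 0, and nothing redefines it for Aim 2.
- **Data available (section 6.0):** for the GSDS, "The 0-10 ratings of depression and anxiety and the summed severity of other 13 symptoms will be derived at each weekly contact". The PROMIS depression and anxiety forms "will be administered at baseline, 13 and 17 week telephone interviews", so they have no week-4 value. Of the mediators, the self-efficacy forms are likewise interview-only: "PROMIS 4-item short forms (sf) will be administered in interviews".

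**The concern.** The second randomisation takes place after week 4, among survivors whose week-4 status marked them as non-responders. Week-4 severity is therefore a measured variable that precedes that randomisation. It can influence both the week-13/17 mediator (self-efficacy, support, burden) and the week-13/17 symptom.

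Randomisation protects the path from group to mediator. It does not protect the path from mediator to symptom, which is observational. With only week-0 severity in the model, whatever week-4 severity adds to both variables is credited to the mediator. The Aim 2 outcome model already uses the later value, so the plan recognises that this contrast has its own starting point, but the mediation paragraph does not carry it over.

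At stake is whether an interval that excludes 0, or fails to, means what the plan says it means for the Aim 2 mediators.

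**Working it through.** **The plan's own figure.** The documents give no figure for mediation. The Aim 2 power statement reproduces: with 60 per group and d = 0.54, power = Φ(0.54 × √(60/2) − 1.96) = Φ(2.958 − 1.96) = 0.84, in line with the stated .80 or greater.

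**Inputs.** From the documents: 60 per group; correlations between pairs of repeated symptom measures of r = 0.36 to 0.77; effect sizes 0.39 and 0.54 (section 4.0). Assumed, because the documents give no value: the group effect on the mediator, a, borrowed from those effect sizes; the link λ between week-4 severity and the mediator; and the form of the non-responder selection.

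**Size of the bias, without selection.** Let severity at weeks 0, 4 and 13 have unit variance and every pair correlation r. Let M = aG + λS4 + √(1−λ²)e. Given week-0 severity and group:

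- covariance of M with the week-13 symptom due to S4 = λ(r − r²)
- variance of M = 1 − λ²r²
- bias in the mediator effect = λr(1−r)/(1−λ²r²)

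For λ = −0.5:

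- r = 0.36: −0.5 × 0.2304/0.9676 = −0.119
- r = 0.77: −0.5 × 0.1771/0.8518 = −0.104

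For λ = −0.3 the values are −0.070 and −0.056. If λ = 0 the bias is 0. If λ is positive the sign reverses. Simulated values agree (−0.112 to −0.121 and −0.101 to −0.112 for λ = −0.5).

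**False mediation, joint-significance test of both paths.** True mediator effect 0, a = 0.54, λ = −0.2 to −0.4, all pairs correlated at r:

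- no selection: about 6% to 24% with week 0 only
- with an assumed non-responder truncation: about 5% to 15%
- with week-4 severity added: about 3% to 5%

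**False mediation, bias-corrected bootstrap as planned.** These runs used 1000 draws rather than 5000, 500 trials per cell and a direct group effect of −0.3 SD. The assumed selection kept week-0 severity above the mean and a fall to week 4 of less than 0.5 SD.

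| r | λ | a | Week 0 | Weeks 0+4 | Week 0, selected | Weeks 0+4, selected |
|---|---|---|---|---|---|---|
| 0.36 | −0.3 | 0.39 | 12.6% | 6.2% | 7.0% | 5.6% |
| 0.36 | −0.3 | 0.54 | 17.0% | 9.8% | 9.6% | 7.8% |
| 0.36 | −0.5 | 0.39 | 20.6% | 8.4% | 8.6% | 5.8% |
| 0.36 | −0.5 | 0.54 | 33.6% | 8.8% | 12.2% | 7.4% |
| 0.77 | −0.3 | 0.39 | 13.0% | 3.8% | 8.6% | 5.2% |
| 0.77 | −0.3 | 0.54 | 20.0% | 7.6% | 14.6% | 10.4% |
| 0.77 | −0.5 | 0.39 | 32.2% | 8.0% | 14.8% | 5.4% |
| 0.77 | −0.5 | 0.54 | 45.6% | 7.4% | 20.8% | 7.4% |

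Adjusting for week 4 alone gave 3% to 11%. The Monte Carlo standard error is about 1 point near 5% and up to 2.5 points near 50%.

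**When nothing is inflated.**

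- λ = 0: 5% to 8% with week 0, against 5% to 10% with week 4. The excess over 5% here comes from the interval method, not from confounding.
- a = 0: 0% to 3% with week 0.

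**Opposite direction.** True mediator effect −0.2, a = 0.54, no selection, 400 trials per cell. With λ = +0.3 or +0.5 the estimate shrinks to between −0.09 and −0.14. Mediation is then detected in 21% to 66% of trials with week 0, against 56% to 85% with week 4. With λ negative the estimate grows to between −0.25 and −0.32.

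**The case against.** A reader might infer that Aim 2 mediation will simply be declared too often. The documents do not support that. It needs a real group effect on the mediator and a mediator that worsens with week-4 severity beyond what week 0 explains. Hypothesis 2 predicts the first, and section 5.0 makes the second plausible by saying that distress can diminish use of the handbook strategies. But neither the sign nor the size of the link is given. Support mobilised by worse symptoms would push the bias the other way.

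A reader might also favour larger rates, such as 9% to 37%. Those come from letting week-0 severity reach the outcome only through week 4, in unselected dyads. That chain makes the week-0 to week-13 correlation r², which is 0.36² = 0.13 at the lower end, below the stated minimum of 0.36. Leaving out selection also ignores that non-responder status narrows week-4 variation.

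Nor does the problem reach the randomised Aim 2 comparison. If week-4 severity is left out, the standard error of the total effect rises by the factor (1+r)/√(1+2r) without selection: 1.04 at r = 0.36 and 1.11 at r = 0.77, and less with selection. The plan does not say that the mediation model's total effect will be reported as the Aim 2 result.

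Finally, the mediators are labelled potential, and other confounding would remain after any fix: mediator and symptom may be measured at the same week, and no adjustment for the mediator's own baseline is named. All of this stands and limits the point. It does not remove the mismatch, which is explicit in both copies of the text.

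**Conclusion.** The mismatch is real and confined to the Aim 2 mediation analyses. A measured confounder of the mediator-to-outcome path, available before the second randomisation, is left out of the model, although the outcome model for the same contrast includes it. The indirect effect may be biased in either direction, or not at all, depending on how the mediator relates to week-4 severity.

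Under the assumptions shown, with a link of −0.2 to −0.4, false mediation is about 6% to 24% without selection and 5% to 15% with it, against 3% to 5% after adjustment. Under the bias-corrected bootstrap with links up to −0.5, it is 13% to 46% and 7% to 21%, against 3% to 11% with week-4 severity. The figures with selection are closer to the Aim 2 population, but the truncation is assumed, and all the rates depend on links that the documents do not supply. The Aim 1 mediation analysis and the randomised group comparisons are unaffected. The correction is worth making because it is almost free.

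**What to change.** In the mediation paragraph of sections 5.0 and 8.0, replace the single covariate statement with:

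*For Aim 1 mediation the covariate is the baseline symptom. For Aim 2 mediation, the GSDS severity of that symptom at week 4, before the second randomisation, is included in addition to its baseline value; for PROMIS outcomes, the PROMIS baseline plus the week-4 GSDS item are used.*

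The text should not describe this pair of covariates as matching the Aim 2 outcome model, because that model names week-4 severity and unspecified covariates, not the baseline value. A short caution that other mediator-outcome confounding may remain would be honest. The cost is one degree of freedom per model. No new data are needed, since the GSDS is already rated at every weekly call.

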6.0 MEASURES/DATA COLLECTION INSTRUMENTS

Describe all forms, questionnaires, instruments or other specific methods used to collect data. Include complete copies of all forms, interview guides, survey questionnaires, in Appendix I.

Measures

Patient Reported Outcomes Measurement Information System (PROMIS)²⁴⁹ measures are suitable for both survivors and caregivers, have been developed using sophisticated measurement techniques, tested with over 21,000 individuals, calibrated to produce T-scores based on the general population, and are available in either English or Spanish. The available short forms have evidence of good reliability and validity.²⁴⁹ Our other measures also have good reliability ($\alpha > .80$)^{41,84,178,205} and validity, have been translated²⁴⁰ and tested with Spanish speaking participants in our pilot studies.³¹

Primary outcomes.

Caregivers' and survivors' symptoms will be measured using the adapted General Symptom Distress Scale (GSDS),^{124,250} a brief instrument that allows for a quick assessment of symptoms, which is especially important during weekly calls. It evaluates 15 symptoms: shortness of breath, nausea, vomiting, pain, sleep difficulties, bowel problems, numbness or tingling, skin rashes or sores, swelling in hands and feet, difficulty concentrating, poor appetite, cough, depression, anxiety, fatigue. Respondents indicate presence of each symptom (yes/no) and rate their severity on the scale from 1 to 10. The ability to manage symptoms is also assessed on a scale from 1=cannot manage to 10=can manage extremely well. The GSDS has good test-retest and internal consistency reliability and predictive and construct validity in both English and Spanish.²⁵⁰ The 0-10 ratings of depression and anxiety and the summed severity of other 13 symptoms will be derived at each weekly contact, baseline, 13, and 17 week interviews.

Survivors' symptom response on depression and/or anxiety during weeks 1-4 as a criterion for rerandomization.

Response will be assessed using the depression and anxiety items of the GSDS administered during weekly calls to survivors. Based on the inclusion criteria and established and validated symptom cut points,²²⁴ survivors will enter with moderate or severe depression and/or anxiety (one symptom or both). The cut-points are anchored in how much symptoms are distressing the participant by interfering with enjoyment of life, social relationships, and general daily activities. Participants indicate the severity/distress from 1 to 10. For depression, the mild category corresponds to a severity score of 1, the moderate category corresponds to scores 2-3, and scores of 4-10 fall into the severe category. For anxiety, the mild category is

severity of 1-3, the moderate category corresponds to scores 4-5, and the severe category is 6-10. Survivors who start at severe or moderate on depression and/or anxiety symptoms at intake and end at a lower category by the week 4 observation will be called **responders to the intervention**.²²⁸ If a symptom was mild at intake, symptom response would not be applicable. Because responders demonstrate substantial improvement anchored to symptom distress after 4 weeks, responders will continue with the SMSH only intervention for another 8 weeks. **Non-responders to the intervention** are survivors who do not respond on either or both symptoms.^{224,251,252} Non-responding survivors and their caregivers will be re-randomized to either continue with the SMSH alone for 8 weeks to give it additional time or add TIP-C for 8 weeks to rigorously test the value added by the more intensive intervention in Aim 2. Total intervention time is 12 weeks.

Caregivers' and survivors' depression and anxiety. PROMIS-short forms 8: depression and anxiety²⁵³⁻²⁵⁶ will be administered at baseline, 13 and 17 week telephone interviews to provide greater detail and precision in the measurement of these outcomes, as compared to single GSDS items administered in weekly calls. We chose 8-item short forms to minimize respondent burden while maintaining measurement precision.

Secondary outcomes. Secondary outcomes are caregivers' and survivors' hospitalizations, urgent care or ED visits during the study. In baseline, week 13 and 17 interviews over the telephone, each dyad member will be asked to recall ED visits and admissions to hospitals and, if they occurred, their reasons and duration. Recall period will be 3 months in baseline and week 13, and 1 month in week 17 interviews. Extensive previous research²⁻⁵ documents self-report is a reliable and valid method to collect health services use data especially when standardized methods are used and the recall period is short, as in this project. Self-report is the only reasonable and cost-effective way to assess healthcare use, as it would be impossible to access health (medical) records across the multiple systems and payers used by participants in this study.

Potential mediators.

Caregivers' and survivors' self-efficacy. PROMIS 4-item short forms (sf) will be administered in interviews.²⁵³⁻²⁵⁶ Self-efficacy specific to symptom management will be captured by the GSDS item described above.

Caregivers' and survivors' social support. PROMIS 4-item-sf for emotional support and PROMIS Informational Support 4a will be used in interviews.²⁵³⁻²⁵⁶

Caregiver Reaction Assessment Tool.²⁵⁷ This caregiver burden tool was developed and validated with caregivers of patients with chronic conditions. It has 5 subscales: impact on schedule, caregiver's esteem, family support, impact on health, and impact on finances, with Cronbach's alphas exceeding 0.70.

Potential Covariates and Future Tailoring Variables. These variables will be assessed during baseline interviews of survivors and caregivers. Demographic characteristics include caregivers' and survivors' age, education, work, ethnicity, race, acculturation, marital status, relationship between survivor and the caregiver, and living arrangement. Comorbidity will be measured with the Bayliss tool that queries the presence of 20 comorbidities,²⁵⁸ and we will also collect height and weight to calculate BMI. The validity and reliability of self-reported height and weight are adequate²⁵⁹⁻²⁶¹, and health risk estimates associated with BMI values are virtually the same, whether based on self-report or measured BMI values.²⁶² Caregiver's activities of survivor care will be measured using a checklist¹⁹, and quality of relationship will be measured using a 6-item index designed to assess the relationship quality. The index has established reliability with samples of married couples²⁶³ and has also been used to capture survivors' perceptions of the quality of relationship with their friend/family caregiver. Preferred language of intervention delivery will be tracked. Receipt and enactment of intervention strategies are measured during weeks 1-12. Receipt will be measured by the number of completed weekly sessions. Enactment of the SMSH strategies is assessed at the beginning of calls during weeks 2-12 as described in section C8c. Enactment of the TIP-C will be measured by tracking the implementation of behaviors discussed and completion of the assigned homework as documented in counselor's field notes for each session. Assessment of survivors' radiation, surgery, chemotherapy, targeted or hormonal therapy (dose, type, dates received), cancer site and stage, and medications (e.g., supportive agents for symptoms) will be collected from health record data corresponding with the time-on-study. Every effort has been made to keep respondent burden to a minimum and to distribute any burden over the course of the study. If needed, we can divide the assessments into two sessions over two days. Yet, few participants requested such accommodations in past studies.

